4.1.4.1 Dose reduction scheme

Treatment related adverse events will be managed by treatment pauses and subsequent dose reductions of afatinib according to the schedule described in Table 4.1.4.1: 1. Dose reductions will apply to individual patients only. Once the dose has been reduced, it cannot be increased later.

Proprietary confidential information.

© 2019 Boehringer Ingelheim International GmbH or one or more of its affiliated companies. All rights reserved.

This document may not - in full or in part - be passed on, reproduced, published or otherwise used without prior written permission.

The investigator is responsible for determining the necessity and frequency of any additional/unscheduled visits as well as the extent of the evaluation (e.g., physical examination, laboratory testing, adverse events, etc.) performed at these visits. At a minimum the investigator should note in the patient's chart when an additional/unscheduled visit occurs and make relevant entries on the AE and medication dispensing eCRFs.

To prevent the development of more severe adverse events, treatment related diarrhoea, nausea and vomiting or rash should be managed early and proactively as described in [Appendix 10.1](#).

Table 4.1.4.1: 1 Dose reduction scheme

AE type and CTC-AE*Grade	Action	Dose Reduction Scheme
Events related to trial drug: 
 • Diarrhoea Grade 2 persisting for 2 or more consecutive days (48 hours) despite adequate anti-diarrhoeal medication/hydration • Reduced renal function to \geq Grade 2 as measured by serum creatinine, proteinuria or decrease in glomerular filtration rate of more than 50% from baseline • Any drug related AE Grade ≥ 3 	Pause treatment until patient has recovered to Grade ≤ 1 or baseline ¹ . Resume treatment at a reduced dose according to the Dose Reduction Column. If patient has not recovered to Grade ≤ 1 or baseline ¹ within 6 weeks trial treatment must be permanently discontinued ² .	Resume with dose reduction by 10mg decrements. If patient cannot tolerate 20mg/day, permanent discontinuation of afatinib should be considered.

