Acute onset and/or unexplained worsening of pulmonary systems (dyspnoea, cough, fever)	Pause afatinib while clinical assessment to exclude ILD is completed.	If ILD is ruled out as a cause of symptoms, grade symptoms and relatedness and report as AEs. If AEs are not related, resume afatinib at current dose. If AEs are drug related, follow directions in row above. If ILD is confirmed, discontinue afatinib.

* The intensity of clinical adverse events graded by the Common Terminology Criteria for Adverse Events v 3.0 (CTC-AE)

1 Baseline is defined as the CTCAE Grade at the start of treatment

2 In the event that the patient is deriving obvious clinical benefit according to the investigator's judgment, further treatment with afatinib will be decided by the investigator.

After treatment pause due to drug related adverse events, treatment with afatinib can be resumed after patient recovers to \leq Grade 1 or baseline. Dose reduction should always follow a treatment pause for drug related AE more than grade 1. In the event of any unrelated adverse events, the investigator may choose to pause the medication to allow the patient to recover, but no dose reduction is required.

Patients will discontinue treatment if they experience deterioration in left ventricular cardiac function (LVEF) to CTCAE Grade ≥ 3 .

Proprietary confidential information.

© 2019 Boehringer Ingelheim International GmbH or one or more of its affiliated companies. All rights reserved.

This document may not - in full or in part - be passed on, reproduced, published or otherwise used without prior written permission.

In the event of any unrelated adverse events, the investigator may choose to interrupt the medication for up to 14 days, but no dose reduction is required and is at the discretion of the investigator. If the medication is continuously interrupted for more than 14 days, the decision to continue with afatinib will be made by the investigator following discussion with the sponsor. Investigator can consider permanently discontinuing the patient from the trial if they have been off trial medication for more than 6 weeks.

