6.2.2 Treatment periods

Safety evaluation visits are to be conducted after the initiation of afatinib, at Day 28 (-7/+2)/Visit 2 and every 28 (-7/+2) days onwards. Additional safety evaluation visits may be conducted as necessary, at the investigator's discretion. The investigator is responsible for determining the necessity and frequency of the additional safety visits as well as the extent of the evaluation (physical examination, laboratory testing, etc.) at each visit.

Investigator must make a phone call to patient on day 15 to enquire about tolerability. If lack of tolerance is suspected, patient must visit site for dose reduction.

Proprietary confidential information.

© 2019 Boehringer Ingelheim International GmbH or one or more of its affiliated companies. All rights reserved.

This document may not - in full or in part - be passed on, reproduced, published or otherwise used without prior written permission.

Table 6.2.2:1 Visit 2/Day 28 (-7/+2) and every 28 (-7/+2) days onwards - treatment and safety evaluation

	The following must be performed and information recorded in the patient's chart	What to include in eCRF
Physical examination	Physical examination results (see Flow Chart).	Verify that this physical examination was performed and record results (see Flow Chart).
Tumour assessment	Tumour Assessment will be based on the assessment of cancer related symptoms and, if available, radiologic assessments as per standard of care at the site. There is no specific schedule for tumour assessment and can be according to standard of care or every 3 cycles.	Tumour assessment where available will be captured in the CRF
Safety Laboratory Testing	Hematology, and Biochemistry examination. See Section 5.2.3 for recommended safety laboratory evaluations and Flow Chart for schedule.	Verify if all recommended safety laboratory testing was performed and that values were acceptable according to the protocol. If not, see Sections: 4.1.4.1 and 5.2.2.1 No lab values are to be recorded on the eCRF.
Urine Examination – Optional	Urine examination. See Section 5.2.3 for recommended urine examinations. Urine Examination is optional at this visit and may be performed at the discretion of the investigator and in accordance to the current standard of care.	Verify if all recommended urine testing was performed. No values from the urine examination are to be recorded on the eCRF.

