This document may not - in full or in part - be passed on, reproduced, published or otherwise used without prior written permission.

Severity (CTCAE Grading)	Description	Specific intervention
EARLY AND LATE XEROTIC SKIN REACTIONS - PRURITUS		
Mild (Grade 1)	Mild or localized	Topical polidocanol cream. Consider oral antihistamines, e.g. diphenhydramine, dimethindene, cetirizine, levocetirizine, desloratidine, fexofenadine or clemastine)
Moderate (Grade 2)	Intense or widespread	See Grade 1 plus oral antihistamines (e.g: levocetirizine 5 mg qd, desloratidine 5 mg qd, diphenhydramine 25–50 mg t.i.d, hydroxyzine 25 mg t.i.d, fexofenadine 60 mg t.i.d). Consider topical steroids, e.g. topical hydrocortisone
Severe (Grade 3)	Intense or widespread and interfering with ADL	See Grade 2
XEROSIS (DRY SKIN)		
Mild (Grade 1)	Asymptomatic	Soap-free shower gel and/or bath oil. Avoid alcoholic solutions and soaps. Urea- or glycerin-based moisturizer. In inflammatory lesions consider topical steroids (e.g. hydrocortisone cream)
Moderate (Grade 2)	Symptomatic, not interfering with ADL	See Grade 1. In inflammatory lesions consider topical steroids (e.g. hydrocortisone cream)
Severe (Grade 3)	Symptomatic, interfering with ADL	See Grade 2. Topical steroids of higher potency (e.g. prednicarbate, mometasone furoate) Consider oral antibiotics
FISSURES		
Mild (Grade 1)	Asymptomatic	Petroleum jelly, Vaseline® or Aquaphor for 30 minutes under plastic occlusion every night followed by application of hydrocolloid dressing; antiseptic baths (e.g. potassium permanganate therapeutic baths, final concentration of 1:10,000, or povidone-iodine baths) Topical applications of aqueous silver nitrate solutions to fissures
Moderate (Grade 2)	Symptomatic, not interfering with ADL	See Grade 1. Consider oral antibiotics.
Severe (Grade 3)	Symptomatic, Interfering with ADL	See Grade 2.
If Grade 2 rash persists for ≥ 7 days despite treatment and is poorly tolerated by the patient, the investigator may choose to pause treatment up to 14 days followed by a reduction in the dose of afatinib according to the dose reduction scheme in Table 4.1.4.1: 1		

Proprietary confidential information.

© 2019 Boehringer Ingelheim International GmbH or one or more of its affiliated companies. All rights reserved.

This document may not - in full or in part - be passed on, reproduced, published or otherwise used without prior written permission.

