10.1.3 Management of mucositis/stomatitis

General and grade specific recommendations are described in [Table 10.1.3: 1](#). For dose adjustment refer to [Section 4.1.4.1](#) and for restrictions on concomitant therapies refer to [Sections 4.2.2](#).

Treatment is supportive and aimed at symptom control. These may include atraumatic cleansing and rinsing with non-alcoholic solutions such as normal saline, diluted salt and baking soda solution (e.g. one-half teaspoonful of salt and one teaspoon of baking soda in one quart of water every four hours); avoidance of agents containing iodine, thyme derivatives and prolonged use of hydrogen peroxide; dietary maneuvers such as promotion of soft, non irritating foods like ice-creams, mashed/cooked vegetables, potatoes and avoidance of spicy, acidic or irritating foods such as peppers, curries, chilies, nuts and alcohol. If the patient is unable to swallow foods or liquids, parenteral fluid and/or nutritional support may be needed. Examples of some of the agents suggested in Table 10.1.3: 1 include: topical analgesics – viscous lidocaine 2%; mucosal coating agents - topical kaolin/pectin; oral antacids, maltodextrin, sucralfate; topical antifungals – nystatin suspension. (Adapted from [P11-09424](#))

Proprietary confidential information.

© 2019 Boehringer Ingelheim International GmbH or one or more of its affiliated companies. All rights reserved.

This document may not - in full or in part - be passed on, reproduced, published or otherwise used without prior written permission.

Table 10.1.3: 1 Grade specific treatment recommendations for afatinib related mucositis/stomatitis

Severity (CTCAE Grading)	Description	Treatment recommendations	Intervention concerning afatinib treatment/dose modification
Mild (Grade 1)	Minimal symptoms; normal diet	Oral rinses with agents such as non-alcoholic mouth wash, normal saline, diluted salt and baking soda solution.	No change.
Moderate (Grade 2)	Symptomatic, but can eat and swallow modified diet	Addition of topical analgesic mouth treatments, topical corticosteroids, antiviral therapy if herpetic infection confirmed, antifungal therapy preferably topical on a case by case basis.	Maintain dose if tolerable; Hold dose if intolerable until recovery to grade ≤ 1 , then restart at the same dose.

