Severe (Grade 3)	Symptomatic and unable to adequately aliment or hydrate orally	Same as for Grade 2; institute additional symptomatic therapy (topical or systemic) as clinically indicated.	Hold dose until recovery to grade ≤ 1 or baseline, then restart at the reduced dose according to Section 4.1.4.1 .
Life threatening (Grade 4)	Symptoms associated with life-threatening consequences	Same as for Grade 2; institute additional symptomatic therapy (topical or systemic) as clinically indicated.	Hold dose until recovery to grade ≤ 1 or baseline, then restart at the reduced dose according to Section 4.1.4.1.

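### After a pause for intolerable afatinib-related Grade 2 stomatitis/mucositis, Section 4.1.4.1 calls for a reduced dose at restart and Table 10.1.3: 1 calls for the same dose

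*Protocol*

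**What the plan says.** Protocol Section 4.1.4.1, in the text below its dose reduction table, sets the rule for resuming afatinib: "Dose reduction should always follow a treatment pause for drug related AE more than grade 1". It names no exception. Earlier in the same section: "Once the dose has been reduced, it cannot be increased later".

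Appendix 10.1.3 covers mucositis and stomatitis. Its introduction says "For dose adjustment refer to" Section 4.1.4.1. Table 10.1.3: 1 then has its own column on afatinib dosing. The Grade 2 entry reads "Maintain dose if tolerable; Hold dose if intolerable until recovery to grade" 1 or below, "then restart at the same dose". The Grade 3 and Grade 4 entries instead say "then restart at the reduced dose according to" Section 4.1.4.1.

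For the other common Grade 2 events, Appendix 10.1 reduces the dose after a pause. Table 10.1.1: 1 pauses and then reduces for Grade 2 diarrhoea lasting 48 hours or more. For persistent, poorly tolerated Grade 2 rash, the note to Table 10.1.2: 2 says that "the investigator may choose to pause treatment up to 14 days followed by a reduction in the dose of afatinib".

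**The concern.** An investigator restarting a patient after a hold for intolerable Grade 2 stomatitis has two written instructions, and they give different doses. Stomatitis/mucositis is one of three common events that Section 4.2.1 names as having specified management, so this is not a remote case.

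Two things are at stake. The first is the patient's dose, since a reduction is permanent. The second is the meaning of two descriptive outputs. SAP Section 7.8.1 tabulates adverse events leading to dose reduction and repeats the table with a stomatitis grouping. SAP Section 7.7 summarises treatment time by dose level. If sites follow different texts, both outputs mix tolerability with each site's choice of instruction.

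**Working it through.** There is no figure in the plan to reproduce. The check is whether one patient can fall under both texts, and whether any other text decides between them.

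**Do both texts apply to the same patient?**

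| Condition | Section 4.1.4.1 | Table 10.1.3: 1, Grade 2 row |
|---|---|---|
| Drug-related event | Yes, by its wording | Yes, the table title limits it to afatinib-related events |
| Grade | Above 1, so 2 is included | 2 |
| Treatment paused | Yes | Yes, if intolerable; a tolerable event is not paused |
| Dose at restart | Reduced | Same |

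Every condition of both is met. The conflict is limited to Grade 2 events that are intolerable and therefore held.

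**Difference in dose.** Section 4.1.4 sets each reduction at 10 mg. From the 40 mg starting dose:
- Section 4.1.4.1: 40 − 10 = 30 mg.
- Table 10.1.3: 1: 40 mg.
- Difference: 10/40 = 25% of the dose, for a patient still on 40 mg.

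**Does another text decide?**
- *Towards reduction:* Section 10.1.3 refers dose adjustment to Section 4.1.4.1. The amendment log shows that Amendment 2 added the general restart sentence, and gives its purpose as clarifying how to resume after a pause. The visible log records no change to Table 10.1.3: 1.
- *Towards the same dose:* Table 4.1.4.1: 1 lists persistent Grade 2 diarrhoea, renal impairment of Grade 2 or higher, and any drug-related event of Grade 3 or higher. Grade 2 stomatitis is not a listed trigger. Section 4.1.4 keeps a patient who meets no listed criterion on 40 mg. The Grade 3 and 4 rows of Table 10.1.3: 1 specify a reduced dose, so the different Grade 2 wording looks intended.
- *Circular:* Section 4.1.4 makes its 40 mg default subject to a reduction being necessary under Section 4.1.4.1, which leads back to the general sentence.

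The pointers divide, and none states an order of precedence.

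**The case against.** The strongest reply is that a specific instruction overrides a general one, so the table row is simply an exception. That is a reasonable way to read a protocol, but this one does not support it: the general sentence says it holds in every case, and the appendix sends dose adjustment back to the section containing that sentence. The opposite reply is that the cross-reference and the Amendment 2 clarification settle the matter in favour of reduction. They carry weight, but they leave unexplained the missing Grade 2 trigger and the table's separation of Grade 2 from Grades 3 and 4. What stands from both replies is that the choice is a clinical one for the sponsor. A reader might infer that the same-dose row is the intended rule; the documents do not establish that.

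It is also fair to object that the effect is narrow. The safety analyses are descriptive, with no hypothesis testing. The adverse event tables show Grades 3, 4, 5 and all grades, so Grade 2 has no column of its own. This limits the importance of the point without removing the contradiction.

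Two stronger readings go too far:
- Section 6.2.2 says of the day-15 call, "If lack of tolerance is suspected, patient must visit site for dose reduction". A reader might infer that this brings the conflict into play for every patient with early intolerance. The sentence mentions neither stomatitis nor a pause and does not cite Section 4.1.4.1.
- A reader might infer that repeated episodes lead to discontinuation under one text and to 40 mg indefinitely under the other. Section 4.1.4 bases all reductions on individual tolerability, and Section 2.3 reports that about half of afatinib-treated patients needed a reduction for common events, so 40 mg is not assured. At the 20 mg floor, Section 4.1.4 makes discontinuation mandatory, whereas Table 4.1.4.1: 1 only asks that it be considered.

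**Conclusion.** The contradiction is real and rests on current text in both places. For a patient on 40 mg with intolerable afatinib-related Grade 2 stomatitis/mucositis that has been held and has recovered, one instruction gives 30 mg and the other 40 mg, and the reduction is irreversible. No assumption is needed for that conclusion.

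The number of patients affected cannot be derived, because the documents give no rate of intolerable Grade 2 stomatitis. Each percentage point of incidence would be 500 × 0.01 = 5 patients at the planned enrolment. Any assumed rate would simply reappear as the difference between the two rules, so none is offered as an estimate of size.

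A reader might infer that the trial's main result is at risk. It is not shown to be: the primary endpoint is the number of patients with serious adverse events, and its definition does not depend on the restart dose. Nor is any effect shown on time to symptomatic progression, whose events are defined in SAP Section 7.5.2 by progression-related reasons for stopping the drug. What is affected is patient dosing and the two descriptive outputs. Correction is worthwhile because the instruction governs dosing and the repair is small.

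**What to change.** The sponsor should decide on clinical grounds which rule is meant and amend one place.

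- **If reduction is intended:** change the Grade 2 row of Table 10.1.3: 1 to the wording already used in its Grade 3 and 4 rows, "then restart at the reduced dose according to" Section 4.1.4.1. This agrees with the cross-reference in Section 10.1.3 and with the Amendment 2 clarification.
- **If the same dose is intended:** add an exception to the restart sentence in Section 4.1.4.1, stating that intolerable Grade 2 stomatitis/mucositis resumes at the unchanged dose as in Table 10.1.3: 1. This agrees with the triggers in Table 4.1.4.1: 1 and with the table's distinction between Grade 2 and Grades 3–4.

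In either case, notify the sites of the rule. The cost is one clause or one table cell in an amendment and a short site memo. No new data and no new SAP display are needed.

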4.1.5 Blinding and procedures for unblinding

Not applicable since this is an open-label trial.

4.1.6 Packaging, labelling, and re-supply

Afatinib will be supplied by BI (or a designated 3rd party drug distribution vendor) as film-coated tablets in High-Density Polyethylene (HDPE) or Polypropylene (PP), child-resistant, tamper-evident bottles. Available dosage strengths will be 40 mg, 30 mg and 20 mg. Each plastic bottle will contain 30 tablets of identical dosage strength. Each bottle will be labelled according to dosage strength and will also include the trial number, medication number, expiry ('use by') dates, and instructions for use. Examples of the labelling of the bottles are found in the ISF.

Adequate supply of afatinib bottles will be dispensed at each visit to last until the next scheduled visit. Afatinib must be dispensed in the original bottles. Patients should be instructed to keep the bottles tightly closed to protect from moisture.

4.1.7 Storage conditions

Afatinib bottles must be kept in a secure, limited access storage area (to authorized people) under storage conditions defined on bottle label until supplied/administered to patient. Temperature logs must be maintained to make certain that the afatinib supplies are stored at the correct temperature. Facilities that have a central temperature alarm do not have to maintain a log; however, a note to file should be kept in the ISF describing the system and the procedure in the event of an alarm. If a site does not have an acceptable central temperature alarm system then the Min/Max temperatures will be documented using a calibrated thermometer with a valid calibration certificate to ensure storage conditions per label. In the event that the temperature would be out of range, this has to be documented in the ISF and reported to the sponsor according to the Storage conditions for Trial Medications (STORM) in the ISF.

Afatinib must be stored in the original package in order to protect from light. Film-coated tablets are humidity sensitive, therefore bottles must be kept tightly closed to protect from moisture. Tablets must be stored according to the storage instructions on the bottle label and in the ISF.

Proprietary confidential information.

© 2019 Boehringer Ingelheim International GmbH or one or more of its affiliated companies. All rights reserved.

This document may not - in full or in part - be passed on, reproduced, published or otherwise used without prior written permission.

4.1.8 Drug accountability

Drug supplies, which will be provided by the sponsor, must be kept in a secure, limited access storage area under the storage conditions defined by the sponsor. Where necessary, a temperature log must be maintained to make certain that the drug supplies are stored at the correct temperature.

The investigator, pharmacist, or investigational drug storage manager will receive the investigational drugs delivered by the sponsor or designee when the following requirements are provided / fulfilled:

- approval of the clinical trial protocol by the Institutional Review Board (IRB)/Ethics Committee (EC),
- availability of a signed and dated clinical trial contract between the sponsor and the investigator /institution,
- approval/notification of the regulatory authority, e.g. competent authority,
- availability of the curriculum vitae of the principal investigator,
- availability of a signed and dated clinical trial protocol, or immediately imminent signing of the clinical trial protocol
- proof of a medical license for the principal investigator,

The investigator, pharmacist, or investigational drug storage manager must maintain records of the product's delivery to the trial site, the inventory at the site, the use by each patient, and the return to the sponsor or alternative disposition of unused product(s).

These records will include dates, quantities, batch/serial numbers, expiry ('use by') dates, and the unique code numbers (i.e., medication numbers) assigned to the investigational product(s) and trial patients. The investigator, pharmacist, or investigational drug storage manager will maintain records that document adequately that the patients were provided the doses specified by the CTP and reconcile all investigational product(s) received from the sponsor. At the time of return to the sponsor and/or appointed CRO the investigator /pharmacist/investigational drug storage manager must verify that all unused or partially used drug supplies have been returned by the clinical trial patient and that no remaining supplies are in the investigator's possession.

